1.0 BACKGROUND AND RATIONALE

1.1 Study Synopsis

This is an open-label, single arm, multicenter phase 2 study of standard salvage high dose cytarabine (HiDAC) on days 1 through 5 followed by a single dose of the humanized monoclonal antibody targeted against cell surface receptor programmed cell death-1 (PD-1), pembrolizumab, on day 14 as induction therapy in patients with relapsed and refractory acute myeloid leukemia (AML). Patients who achieve at least a partial response (PR) post-induction will continue on pembrolizumab every 3 weeks for up to 1 year of maintenance therapy. We plan to enroll 37 patients in a Simon's two-stage design.

The hypothesis of this study is that HiDAC followed by pembrolizumab will be effective in relapsed and refractory AML with a combined complete remission (CR)/CR with incomplete recovery (CRi) rate of $\geq 40\%$, superior to a historical control of 20%. We also hypothesize that the rate of unacceptable toxicity associated with HiDAC followed by pembrolizumab will not significantly exceed 20% (see section 2.4.2). Secondary endpoints include toxicity of this combination when used as induction, overall objective response rate (CR+CRi +PR) post-induction, toxicity of pembrolizumab maintenance in those patients with a response after induction, and progression-free survival (PFS), relapse-free survival (RFS) and overall survival (OS) in patients who receive maintenance pembrolizumab. We will also explore for an association between potential immune biomarkers and clinical outcomes with pembrolizumab. The overarching goals of these correlative studies are: 1) to identify and characterize mechanisms involved in T cell dysfunction in AML, 2) to identify potential predictive biomarker candidates to allow better selection of AML patients who may benefit from pembrolizumab, and 3) to identify new pathways that could be targeted to enhance the efficacy of pembrolizumab in AML.

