4.0 TREATMENT PLAN

4.1 Schema

¹During Maintenance, bone marrow biopsy to be done after every 4th cycle of pembrolizumab for year 1, and every 8th cycle of pembrolizumab during years 1-2.

²See Time and Events Table for schedule of serial blood samples for correlative research

This is a phase 2, open-label, multicenter, single-arm study evaluating HiDAC salvage induction chemotherapy followed by pembrolizumab in the relapsed/refractory AML setting. Toxicity will be assessed during treatment via NCI CTCAE v4.0. Tumor specimens from a pre-study bone marrow biopsy and post-treatment bone marrow biopsies as well as serial blood samples will be collected for correlative studies.

Pembrolizumab 200 mg is administered IV once as monotherapy, 14 days after the initiation of HiDAC salvage induction chemotherapy. Patients who have a response (i.e., PR/CR/CRi) to induction phase will receive maintenance pembrolizumab at 200 mg IV every 3 weeks for up to 2-years of maintenance therapy (i.e., beginning on day 1 of maintenance).

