4.3 Maintenance Phase

Patients who achieve a PR, CR, or CRi (see section 6.9) will receive pembrolizumab 200 mg IV Q3weeks on an outpatient basis. In order to qualify for pembrolizumab maintenance, all patients will be required to meet laboratory eligibility criteria as outlined in Section 3.1.7 and prior drug-related toxicities must have resolved to \leq grade 1 or baseline. Any patient experiencing unacceptable toxicity during induction, as defined in section 2.4.2, will not be eligible for maintenance, but will be discontinued from protocol-directed therapy and followed-up per protocol. In those who have achieved a CR or PR, pembrolizumab maintenance will begin 10-60 days following full hematologic recovery (absolute neutrophil count \geq 1,000/mcL and platelet count \geq 100,000/mcL). Patients who achieve CRi will begin maintenance pembrolizumab 10-60 days following a bone marrow biopsy disease assessment after induction phase (a repeat bone marrow biopsy should be performed if CRi patients subsequently achieve full hematologic recovery prior to pembrolizumab maintenance, as detailed in Section 4.2: Induction Phase). Patients eligible to receive maintenance therapy should begin maintenance as early as possible (\geq 10 days after hematologic recovery occurs, and once recovery from drug-related toxicities \leq grade 1 or baseline). Those who do not receive maintenance therapy by day 60 of hematologic recovery or by day 60 of post-induction bone marrow biopsy in CRi patients will be taken off study protocol.

All patients who continue pembrolizumab maintenance therapy will have disease assessments with bone marrow biopsies after every 4 cycles of treatment (i.e., every 12 weeks) for the first year, and then after every 6 cycles of treatment (i.e. every 18 weeks) during years 1-2. If there is suspicion for disease progression, a disease assessment via bone marrow biopsy will occur at any time during the maintenance phase. Patients will continue pembrolizumab 200 mg IV Q3weeks

for up to 2 years (i.e., 34 cycles of treatment) until disease progression, unacceptable toxicity, receipt of allogeneic stem cell transplantation or investigator and/or patient chooses to discontinue treatment.

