4.3.1 Toxicities and Dose Modifications for Pembrolizumab Maintenance

Adverse events (both non-serious and serious) associated with pembrolizumab exposure may represent an immunologic etiology. These adverse events may occur shortly after the first dose or several months after the last dose of treatment. Pembrolizumab must be withheld for drug-related toxicities and severe or life-threatening AEs as per Table 3 below. See section 4.4 for supportive care guidelines, including use of corticosteroids.

Dosing interruptions are permitted in the case of medical / surgical events or logistical reasons not related to study therapy (e.g., elective surgery, unrelated medical events, patient vacation, and/or holidays). Subjects should be placed back on study therapy within 3 weeks of the scheduled interruption, unless otherwise discussed with the Sponsor. The reason for interruption should be documented in the patient's study record.

If a dose of pembrolizumab is delayed, then the subsequent dose should be administered 3 weeks later. Patients may receive up to 1 year of treatment with pembrolizumab beginning on day 1 of maintenance therapy. In the event of dose delays/interruptions, subjects may not receive more than 1 total year of treatment beginning with day 1 of maintenance therapy.

Table 3. Dose Modifications

General instructions:				

 1. Corticosteroid taper should be initiated upon AE improving to Grade 1 or less and continue to taper over at least 4 weeks. 2. For situations where pembrolizumab has been withheld, pembrolizumab can be resumed after AE has been reduced to Grade 1 or 0 and corticosteroid has been tapered. Pembrolizumab should be permanently discontinued if AE does not resolve within 12 weeks of last dose or corticosteroids cannot be reduced to ≤ 10 mg prednisone or equivalent per day within 12 weeks. 3. For severe and life-threatening irAEs, IV corticosteroid should be initiated first followed by oral steroid. Other immunosuppressive treatment should be initiated if irAEs cannot be controlled by corticosteroids. 				
Immune-related AEs	Toxicity grade or conditions	Action taken to pembrolizumab	irAE management with corticosteroid and/or other therapies	Monitor and follow-up

Amendment 07

	(CTCAEv4.0)			

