4.6 Duration of Therapy

In the absence of treatment delays due to adverse event(s), treatment may continue until one of the following criteria applies:

- Failure to achieve a PR, CR, or CRi after induction phase
- Disease progression/relapse at any time during induction or maintenance phase
- Receipt of allogeneic stem cell transplantation
- Completion of 2 years of pembrolizumab maintenance therapy
- Intercurrent illness that prevents further administration of treatment
- Unacceptable adverse event(s) while on pembrolizumab therapy as defined in section 2.4.2
- Patient decides to withdraw from study
- Patient unable to comply with protocol requirements
- General or specific changes in the patient's condition that render the patient unacceptable for further treatment in the judgment of the investigator.

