³ Patients in $\geq \text{PR}$ based on BM biopsy may continue to receive pembrolizumab every 21 days +/- 3 days (1 cycle) until maintenance treatment duration totals 1 year (see section 4.3 for additional details), disease progression, or intolerable toxicity, whichever occurs first. Pembrolizumab will start 10-60 days post full hematologic recovery in those who achieve PR or CR, and 10-60 days post the post induction bone marrow biopsy in those who achieve CRi. Patients who do not achieve at least a PR, or receive pembrolizumab maintenance by day 60 of hematologic recovery (or day 60 post-induction bone marrow biopsy in CRi patients) will be taken off of protocol-mandated therapy and followed up per protocol.

⁴ This end of treatment (EOT) visit should occur in patients when they stop treatment whether due to disease progression, unmanageable toxicity, or they have reached 2 years of treatment, and will take place ~30 days post last dose of pembrolizumab. Patients who experience $\geq \text{Grade 2}$ treatment-related adverse event will be contacted every 2 weeks until the event is resolved to Grade 0 or 1, determined to be irreversible by the investigator, or until the patient begins an alternate form of drug treatment.

⁵ The first long-term follow-up visits will take place ~60 days after the EOT visit (+/- 15 days) and will focus on any serious adverse events (SAEs) or any grade of Events of Clinical Interest (see section 7.3.4.1) that occur within 90 days of the end of pembrolizumab (or prior to start of new anti-cancer therapy). Any such events must be recorded. Subsequent long-term follow up visits will take place at a schedule as per institutional standard of care (i.e., usually every ~3-6 months) and will be limited to history of any subsequent cancer treatments, an assessment of any SAE's considered to be possibly or probably related to study treatment until resolution, and survival status.

⁶ Complete history at baseline only, thereafter focused history on symptoms/toxicity. Physical exam to include height (baseline only), weight (D1 and D14 of cycle 1, D1 of all cycles of maintenance pembrolizumab and all follow-up visits) and vital signs

⁷ Serum or urine B-HCG within 72 hours prior to D1 of HiDAC and prior to D14 pembrolizumab, and only if clinically appropriate; if the urine test is positive or cannot be confirmed as negative, a serum pregnancy test will be required.

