8.0 STATISTICAL CONSIDERATIONS

8.1 Study Design and Sample Size

This is a multi-center prospective open-label single arm phase 2 study assessing the activity of age-adjusted HiDAC (<60 years: 2 gm/m² IV Q12hours days 1-5; ≥60 years: 1.5 gm/m² IV Q12hours days 1-5) salvage induction treatment followed by pembrolizumab 200 mg IV on day 14 for relapsed or refractory AML patients.

The subjects who achieve a response (CR, CRi, or PR) to induction phase HiDAC followed by pembrolizumab 200 mg IV on day 14, as assessed by standard international European LeukemiaNet Guidelines in AML,²¹ will receive pembrolizumab 200 mg IV Q3weeks of maintenance therapy beginning 10-30 days following full hematologic recovery from induction phase. Maintenance treatment will continue until disease progression, toxicity, physician and/or patient discretion, or up to 1 year of treatment.

Simon's like two-stage design with relaxed stopping for futility will be used.⁵³ The null hypothesis that the true CR rate (CR/CRi) for HiDAC followed by pembrolizumab is 20% will be tested against a one-sided alternative hypothesis. In this study, "relaxed stopping" refers to inclusion of PR in the first stage as some of these PRs may convert to a CR during maintenance. In the first stage, 19 patients will be enrolled. If the number of patients who achieve a CR/CRi plus the number of patients with PR is equal to 4 or fewer in these 19 patients, the study will be stopped. Otherwise, 18 additional patients will be enrolled for a total of 37 patients. The null hypothesis will be rejected if 12 or more CR/CRi's are observed in 37 patients.. Assuming that the PR rate has a uniform distribution, Uniform (0, 0.05), under H₀, this design yields a type 1 error rate of at most 5% and power of at least 84% when the true CR rate for HiDAC followed by pembrolizumab is 0.4.

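### Current text caps pembrolizumab maintenance at both 1 year and 2 years; more narrowly, the removal rule opposes Table 3 for some hypothyroidism events

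*Combined protocol and SAP*

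**What the plan says.** All of the following is current body text of the combined protocol and SAP (Amendment 7), not the amendment log.

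**Ceiling of 1 year**

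- Section 1.1: responders "will continue on pembrolizumab every 3 weeks for up to 1 year of maintenance therapy".
- Section 4.3.1, without condition: "Patients may receive up to 1 year of treatment with pembrolizumab beginning on day 1 of maintenance therapy".
- Section 4.3.1, for delays: "In the event of dose delays/interruptions, subjects may not receive more than 1 total year of treatment beginning with day 1 of maintenance therapy".
- Section 6.1, footnote 3: dosing may go on "until maintenance treatment duration totals 1 year (see section 4.3 for additional details").
- Section 8.1: maintenance runs to progression, toxicity, discretion, "or up to 1 year of treatment".

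**Ceiling of 2 years**

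- Section 4.1: "every 3 weeks for up to 2-years of maintenance therapy", counted from day 1 of maintenance.
- Section 4.3: "for up to 2 years (i.e., 34 cycles of treatment) until disease progression" or another listed stopping reason.
- Section 4.6, as a criterion that ends treatment: "Completion of 2 years of pembrolizumab maintenance therapy".
- Section 6.1: the maintenance column heading and footnote 4 both refer to 2 years.
- Section 6.4.2 sets out a visit schedule for Year 2, and 6.5 defines the end-of-treatment visit for patients who complete 2 years.

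**Toxicity**

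- Section 4.6 ends treatment for an unacceptable adverse event on pembrolizumab as defined in 2.4.2, and 4.8 says patients will be removed when any 4.6 criterion applies.
- Section 2.4.2 covers drug-related non-hematologic toxicity of grade 4 or above (infection excluded), and grade 3 persisting more than 7 days with supportive care. The grade 3 exceptions do not include hypothyroidism.
- Table 3 in 4.3.1 and Appendix B give one action for hypothyroidism of grades 2 to 4: continue pembrolizumab, with thyroid hormone replacement.

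**The concern.** A responder who reaches month 12 of maintenance must stop under 4.3.1 and may go on under 4.3. Both limits are ceilings, so stopping at month 12 breaches neither, while dosing in month 13 breaches 4.3.1. Section 9.6 requires the study to be run as the approved protocol describes, except in emergencies. A multicenter trial therefore has an instruction that sites can resolve in different ways, with the same conduct counted as compliant under one section and as a deviation under another. The maintenance toxicity data for objective 2.2.4 could then mix two maximum exposures.

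The second issue has the same form. For one named toxicity, at a defined severity, one rule removes the patient from protocol therapy and another tells the site to continue.

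**Working it through.** **1. The plan's own cycle count.** Section 4.3 equates 2 years with 34 cycles. With 21-day cycles, 730 / 21 = 34.76, so 34 full cycles: reproduced. One year gives 365 / 21 = 17.38, so 17 full cycles. The figure of 34 fits only the 2-year limit.

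**2. Maximum exposure.** At the stated 200 mg per cycle: 17 × 200 = 3,400 mg and 34 × 200 = 6,800 mg, a twofold difference. Counting infusions with a dose on day 1 gives 18 and 35, and the contrast is essentially the same.

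**3. Can the limits be read as different clocks?** No. Sections 4.1 and 4.3.1 both count from day 1 of maintenance. Nor can the 1-year cap be confined to patients with dose delays: that covers the second sentence in 4.3.1, but the first is unconditional. Footnote 3 states 1 year, refers the reader to 4.3, which states 2, and is attached to a column headed 2 years.

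**4. How many patients could be affected (illustration).** Only those still on maintenance at month 12.

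- Responders: 37 × 0.20 = 7.4 (CR/CRi 20%, PR 0%) to 37 × 0.45 = 16.65 (CR/CRi 40%, PR 5%). The 20% and 40% are the hypotheses in 8.1; 0 to 5% is the PR range that 8.1 assumes under the null.
- Still in response at maintenance month 12: S = 0.5^((12 + lag) / median), assuming exponential durations. The median is 5 months, or 9 as the upper bound of the figure below 9 months; both are in 1.3 and come from regimens without pembrolizumab. The lag is the 10 to 60 days in 4.3, or 0.33 to 1.97 months.
- Median 5: S = 0.181 to 0.144. Median 9: S = 0.387 to 0.341.
- Loss to transplant: 0 to 50%, an assumption, since no rate is given. No other exits are modelled.
- Low end: 7.4 × 0.144 × 0.5 = 0.53. High end: 16.65 × 0.387 = 6.4.

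**5. Does duration enter the design figures?** With p the CR/CRi rate and r the PR rate, the probability of rejection under 8.1 is the sum over c of P(C1 = c) × P(C1 + PR1 ≥ 5 given c) × P(C2 ≥ 12 − c). Here C1 ~ Bin(19, p), PR1 given c ~ Bin(19 − c, r/(1 − p)) and C2 ~ Bin(18, p). At p = 0.2 this gives 0.0471 (r = 0) to 0.0496 (r = 0.05), averaging 0.0485 over the uniform prior. At p = 0.4 and r = 0 it gives 0.841. These agree with the stated at most 5% and at least 84%, and no term involves maintenance duration.

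**6. Hypothyroidism, case by case (drug-related events).**

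| Event | Meets 2.4.2? | 4.6 / 4.8 | Table 3, Appendix B |
|---|---|---|---|
| Grade 2 | No | No removal | Continue |
| Grade 3, not persisting more than 7 days with supportive care | No | No removal | Continue |
| Grade 3, persisting more than 7 days with supportive care | Yes | Remove | Continue |
| Grade 4 | Yes | Remove | Continue |

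Only the last two rows conflict.

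**The case against.** The best reply on duration is that the amendment log records a change from 1 to 2 years (Amendments 4 and 7), so the 1-year sentences look like text that was not revised rather than a competing design. That is a fair account of how the conflict arose. It does not remove it: the log describes changes, sites work from the operative sections, and one of those, 4.3.1, forbids more than 1 year in terms. It would, however, be wrong to say that the documents give no indication of what was intended.

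It is also fair that objective 2.2.4 is descriptive, that exposure already varies through progression, transplant and discretionary stopping, and that the upper figure of 6 is an extreme.

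Three stronger readings are tempting and are not supported.

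- *The primary endpoint is materially compromised.* Section 6.9 counts a PR that becomes CR on maintenance as an overall CR, so duration could affect how long conversions are observed. But 6.9 sets no time limit under either duration, which makes the missing cut-off a separate matter. At a 5% PR rate the expected number of PR patients is 37 × 0.05 = 1.85; this is an expectation, not a maximum. Applying step 4 leaves 1.85 × 0.144 × 0.5 = 0.13 to 1.85 × 0.387 = 0.72 on maintenance at month 12, before any chance of a first conversion in year 2. The documents give no conversion rate.
- *Table 3 contradicts 4.6 generally.* For grade 3 colitis, type 1 diabetes or hyperglycemia, grade 3 to 4 hypophysitis and hyperthyroidism, and other grade 3 immune-related events, Table 3 provides for withholding and permits resumption, without requiring it. Precedence over 4.6 is unstated, but these rows are not in direct opposition.
- *Many patients would meet the hypothyroidism conflict.* Section 5.1.6 reports 34 of 411 melanoma patients (8.3%) with hypothyroidism, without a breakdown by grade, and none discontinued for it. That figure cannot be turned into a count of events meeting 2.4.2.

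**Conclusion.** The contradiction on duration stands: two incompatible ceilings in operative text, from the same starting day, differing by a factor of two (about 17 versus 34 full cycles). It rests on the wording and not on any modelling. The number of patients touched is small, illustratively about 0.5 to 6 of 37. That range depends on exponential response durations borrowed from regimens without pembrolizumab, an assumed 0 to 50% loss to transplant and no other exits. The stated type 1 error, power and N = 37 are unaffected. Any effect on the primary endpoint is small under the PR assumption in 8.1 and is not quantified here.

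The hypothyroidism conflict also stands, as a narrower point limited to drug-related events that are grade 4, or grade 3 persisting more than 7 days with supportive care. Its frequency cannot be derived from the documents and is probably low.

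The case for correction is that the protocol gives opposing instructions on how long to dose and on whether to stop for a named toxicity, and that the remedy is cheap.

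**What to change.** Issue one clarifying amendment that:

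- states the maintenance duration once and reconciles it across 1.1, 4.1, 4.3, 4.3.1 (both sentences), 4.6, the Time and Events column heading and footnotes 3 and 4, 6.4.2, 6.5 and 8.1;
- reconciles 4.6, 4.8 and 2.4.2 with Table 3 and Appendix B for hypothyroidism;
- aligns two lesser mismatches at the same time: the maintenance start window (10 to 30 days in 8.1; 10 to 60 in 4.3 and footnote 3) and the year-2 marrow interval (every 8th cycle in the 4.1 footnote; every 6th in 4.3, 6.4.2.2 and footnote 11).

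Which duration and which clinical rule stand is for the sponsor to decide. The cost is one amendment, with no added patients or procedures.

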4.4 Rescue Medications & Supportive Care

4.4.1 Cytarabine-related Kerato-conjunctivitis

To prevent cytarabine-related kerato-conjunctivitis, dexamethasone 0.1% ophthalmic eye drops (or per institutional formulary) must begin at least 1 hour prior to cytarabine initiation. Eye drops should be performed every 6 hours to both eyes until day 12 of induction phase treatment.

4.4.2 Antiemetics

Antiemetics will be used according to standard practices with the exception of systemic steroids (i.e., dexamethasone). Use of systemic steroids during this trial is not allowed. Any 5-hydroxytryptamine (5-HT₃) receptor inhibitor (e.g.,

ondansetron) combined with haloperidol or prochlorperazine as needed, will be used during chemotherapy infusions and during pembrolizumab administration, as needed.

4.4.3 Antimicrobial prophylaxis

Patients will receive prophylaxis against gram-negative gastrointestinal infections (GI), candidiasis, and herpes simplex virus (HSV), while patients are aplastic, during induction phase, and as per standard of care. Antimicrobial prophylaxis will only occur in the maintenance phase if patients develop neutropenia (absolute neutrophil count <500/mcL).

4.4.4 Colony Stimulating Factors

The routine use of colony stimulating factors is not allowed. The use of colony stimulating factors in the presence of severe or life-threatening infection should be discussed with the principal investigator before implementation.

4.4.5 Prevention and Management of Tumor Lysis Syndrome (TLS)

Tumor lysis occurs as part of initial cytoreductive therapy. In its most extreme form, TLS, is characterized by hyperuricemia, hyperphosphatemia, increased lactate dehydrogenase (LDH), coagulopathy, and a potential cytokine release syndrome.

Tumor lysis labs consisting of basic metabolic panel, uric acid, calcium, and phosphate must be drawn a minimum of twice daily at least through day 5 of chemotherapy and once daily through day 10, until maximum tumor lysis has abated. The following precautionary and prophylaxis regimens are suggested prior to and during initial chemotherapy administration:

- To prevent hyperuricemia, all patients without known allergy will receive allopurinol 300-600 mg PO qday 24 hours prior to beginning chemotherapy and the allopurinol 300-600 mg PO qday continuing through the period of maximal tumor lysis (at least through day 8) or other antiuricemia regimen per institutional practice. Rasburicase may be used per institutional policy for hyperuricemia. Screening for G6PD deficiency should be obtained in susceptible populations before beginning rasburicase.
- To decrease the risk of hyperphosphatemia, an oral phosphate binder per institutional practice (e.g. sevelamer 400-800 mg) will be administered orally every 8 hours beginning on day 1 of induction phase and continued as tolerated until maximum tumor lysis has occurred (at least day 8).
- Cytokine release syndrome can occur shortly after completion of drug infusion, accompany severe TLS, and present with fever, bronchospasm with dyspnea and/or respiratory distress, altered blood pressure, myalgias, arthralgias, tumor pain and/or urticarial rash. Any patient with cytokine release syndrome should receive 20 mg dexamethasone (or equivalent steroid) IV immediately. Pembrolizumab must begin at least 7 days after the last dose

of steroids for cytokine release syndrome.

